10.2. Clinical Laboratory Assessments

Blood samples are drawn for the following analyses: complete blood count, gamma glutamyl transferase (GGT), total bilirubin, alkaline phosphatase (ALP), aspartate transaminase (AST), alanine transaminase (ALT), and albumin, creatine kinase (CK), and cystatin C.

Laboratory test results and change from baseline are summarized by analysis visit.

CTCAE grade 3 or higher lab test results will be considered potentially clinically significant. These results are summarized and presented in a data listing.

Shift tables to summarize changes from baseline to each visit in CTCAE categories are tabulated. Shift from baseline to most severe CTCAE category during the study is also summarized.

The Baseline for the laboratory parameters will be taking from EOS Laboratory value of the Parent study 079.

Laboratory values out of normal range, in particular, panic laboratory parameter / values will be listed.

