#### **7.1.4. Early Withdrawal from Treatment and Safety Follow-up Period**

Subjects who prematurely discontinue the main study should be strongly encouraged to complete the final efficacy evaluations scheduled for Week 208/EOT as applicable, and the safety follow-up evaluations scheduled for the Week 210/EOS visit (4 weeks following the last dose).

Subjects who withdraw prior to week 104 will not be eligible to participate in the OLE.

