### 2. Study Enrollment

All subjects participating in the Open Label Extension must have completed treatment through the primary endpoint and completed the EOT visit on the parent pamrevlumab DMD study. The

study investigator must consider the subject medically stable for continued treatment. Written consent/assent by the subject and/or their legal guardian (as required by the site's IRB) must be obtained prior to the subject's participation in the OLE. Administration of current approved DMD therapies is allowed during the OLE treatment period if deemed acceptable by the investigator. Administration of such therapies must be withheld for three hours after the end of pamrevlumab infusion.

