2. STUDY DESIGN

This study is designed as the open-label extension (OLE) of the main study FGCL-3019-079. All subjects participating in the OLE must have completed treatment through the primary endpoint and completed the End of Treatment (EOT) visit of the main study FGCL-3019-079.

Each subject in the OLE receives pamrevlumab (35 mg/kg, every 2 weeks) for up to 208 weeks. The dosing period began on the first day of dosing with study treatment (Day 1) in the OLE, which is to be conducted simultaneously with, or within 7 days after the parent study EOT visit. The dosing period continued until Week 208/EOT.

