5.4.3. Definition of Baseline

- Baseline for the OLE period is the acceptable value from the last visit on or before the first dose date in OLE.

- Baseline for main study period is defined the same as in SAP for the main study period.

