13. CHANGES FROM PROTOCOL

- The date of the first dose in the OLE period will be considered as the date of Day 1 for all analyses during the OLE period, instead of Day 0.
- Efficacy parameters, including change from baseline of the main study in ppFVC, PUL, grip strength, LVEF%, and cardiac MRIs including cardiac fibrosis score assessed by Late Gadolinium Enhancement (LGE), and Myocardial Circumferential Strain [Global Circumferential Strain (GCS)], will be analyzed at Week 48/52, Week 96/104, etc. in the OLE period using Mixed Model for Repeated Measures (MMRM) additionally.

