15. APPENDICES

APPENDIX 1. ANALYSIS VISIT WINDOWS

Table 1: Assessment Windows for PFT

Analysis Visit	Window
Baseline	Value at the visit on or prior to the first dose of study drug Target day=1, window = $[L_0, H_0] = [-, 1]$
Week X	$X = 24*K$, $k=1, 2, \dots, 7$ Target day = $7 * X + 1$ Window = $[L_K, H_K] = [H_{K-1}+1, \text{Target Day}+24*7/2-1]$
Week 192	$[L_8 = H_7+1 = 1261, **]$

** There will be no upper bound; all assessments will be included.

Table 2: Assessment Windows for Muscle Function Tests

Analysis Visit	Window
Baseline	Value at the visit on or prior to the first dose of study drug Target day=1, window = $[L_0, H_0] = [-, 1]$
Week X	$X = 12*K$, $k=1, 2, \dots, 16$ Target day = $7 * X + 1$ Window = $[L_K, H_K] = [H_{K-1}+1, \text{Target Day}+12*7/2-1]$
Week 204	$[L_{17} = H_{16} +1=1387, **]$

** There will be no upper bound; all assessments will be included.

Table 3: Assessment Windows for Cardiac MRI

Analysis Visit	Window
Baseline	Value at the visit on or prior to the first dose of study drug Target day=1, window = $[L_0, H_0] = [-,1]$
Week X	$X = 52*K$, $k=1, 2, 3$ Target day = $7 * X + 1$ Window = $[L_K, H_K] = [H_{K-1}+1, \text{Target Day}+52*7/2-1]$
Week 208	$[L_4 = H_3+1= 1275, **]$

* There will be no upper bound; all assessments will be included.

Table 4: Assessment Windows for Vital Signs

Analysis Visit	Window
Baseline	Baseline are defined as the average of last Screening and Week 0 pre-infusion measurements. Target day=1, window = $[L_0, H_0] = [-,1]$
Week X	$X = 2*K$, $k=1, 2, 3, \dots, 105$ Target day = $7 * X + 1$ Window = $[L_K, H_K] = [H_{K-1}+1, \text{Target Day}+6]$

*The last visit window will not have an upper bound; all assessment will be included.

Table 5: Assessment Windows for Labs Tests

Analysis Visit	Window
Baseline	Value at the visit on or prior to the first dose of study drug Target day=1, window = $[L_0, H_0] = [-,1]$
Week X	$X = 24*K$, $k=1, 2, \dots, 8$ Target day = $7 * X + 1$ Window = $[L_K, H_K] = [H_{K-1}+1, \text{Target Day}+24*7/2-1]$
Week 210	$[L_9 = H_8+1= 1408, **]$

* There will be no upper bound; all assessments will be included.

All scheduled and unscheduled assessments are included in the by-visit summary. If more than two assessments are available in the same window, the last assessment will be used in the by- visit summary.

If any visit is missed, assessments should be performed as soon after the missed visit as feasible. Missed infusions will not be replaced.

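### SAP 10.2 takes the OLE laboratory baseline from the parent-study EOS visit, which rollover subjects would not normally reach before OLE dosing, and this contradicts SAP 5.4.3 and Table 5

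*SAP*

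**What the plan says.** **Laboratory baseline.** SAP 10.2 plans laboratory change from baseline by visit, CTCAE shifts from baseline to each visit, and the shift to the worst category. It then gives its own baseline rule: "The Baseline for the laboratory parameters will be taking from EOS Laboratory value of the Parent study 079".

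Two other places in the SAP give a different rule:
- Section 5.4.3: "Baseline for the OLE period is the acceptable value from the last visit on or before the first dose date in OLE".
- Appendix 1, Table 5 (laboratory tests): "Value at the visit on or prior to the first dose of study drug", with a window closing on Day 1. Section 13 fixes that day: "The date of the first dose in the OLE period will be considered as the date of Day 1 for all analyses" in the OLE period.

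**Timing of the visits.** OLE entry requires that the subject has "completed the EOT visit on the parent pamrevlumab DMD study" (Protocol Appendix 6, Study Enrollment). It does not require a parent EOS visit. SAP Section 2 describes the first OLE dosing day as one "which is to be conducted simultaneously with, or within 7 days after the parent study EOT visit". Protocol 7.1.4 describes the parent EOS as "the Week 210/EOS visit (4 weeks following the last dose"), and Protocol 7.1.5 allows ±7 days around the 4 weeks.

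**Vital signs.** Appendix 1, Table 4 has its own rule: "Baseline are defined as the average of last Screening and Week 0 pre-infusion measurements".

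**The concern.** A baseline for the extension has to be measured before the first extension dose. The parent EOS visit is an off-drug follow-up visit, and a subject who continues on drug has no off-drug follow-up at that point. Protocol 7.1.5 counts the final safety assessment from the last dose of pamrevlumab, so for a continuing subject it moves to the end of the OLE.

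A programmer who follows 10.2 literally would therefore find no baseline for most or all rollover subjects, or would pick a sample taken after OLE dosing began. The labels make the second outcome possible. The main study and the OLE share one study number and one clinical study report, and both schedules call the final visit Week 210/EOS.

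The outputs at stake are the laboratory change-from-baseline tables and the two CTCAE shift tables.

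**Working it through.** This is a calendar check, counted in days from the last main-study infusion.

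**Inputs**
- Last infusion for a full-length subject: Week 206, since none is given at Week 208/EOT (Protocol Appendix 4, note j).
- Dosing visit window ±2 days (Protocol 7.1.2).
- EOS 4 weeks ±7 days after the last dose (Protocol 7.1.5).
- OLE Day 0 at EOT or up to 7 days later (SAP 2; Protocol Appendix 6).

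**Reproducing the stated EOS week.** 206 + 4 = Week 210, as the protocol gives it.

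**EOS against the first OLE dose**

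| Event | Nominal day | With windows |
|---|---|---|
| Parent EOT | (208 − 206) × 7 = 14 | 12 to 16 |
| First OLE dose | 14 to 14 + 7 = 21 | 12 to 16 + 7 = 23 |
| Parent EOS | 4 × 7 = 28 | 21 to 35 |

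Nominal EOS minus first OLE dose is 28 − 21 = 7 to 28 − 14 = 14 days, so EOS comes after OLE dosing starts. The ranges meet only on days 21 to 23, with a late OLE start and an early EOS.

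**Would reading EOS as EOT repair the sentence?** No. The main schedule marks no central laboratory sample at Week 104 (Appendix 3) or at Week 156 or 208/EOT (Appendix 4), and the OLE schedule marks none at Day 0. Local samples are drawn before MRI, but Protocol 7.2.7 keeps them out of the study database except for hematocrit.

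**What the 5.4.3 and Table 5 rule delivers.** Scheduled central laboratory weeks near transition are 96, 116, 128, 140, 152, 168, 180, 192 and 204. Age of the last scheduled sample at the first OLE dose is 7 × (EOT week − laboratory week), plus 0 to 7 days:

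| EOT week | Last laboratory week | Age in days |
|---|---|---|
| 104 | 96 | 7 × 8 = 56 to 63 |
| 156 | 152 | 7 × 4 = 28 to 35 |
| 208 | 204 | 7 × 4 = 28 to 35 |

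The protocol moves subjects over within 2–3 infusions of the amendment's approval, after at least 104 weeks. If that can happen at any dosing visit (an assumption), the longest gap is at Week 114: 114 − 96 = 18 weeks, plus up to 7 days.

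**Vital signs.** The OLE schedule has no Screening column, but it marks vital signs at Day 0, taken pre-infusion. Only one of the two visits in Table 4 is therefore absent. Main-study screening preceded all study drug and lies at least 104 weeks back, so averaging it with Week 0 would mix untreated and long-treated values. It would also depart from 5.4.3.

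**The case against.** The strongest reply is that the SAP already contains a workable laboratory baseline in two places, one of them specific to laboratory tests, with Day 1 tied to the first OLE dose. On that view the 10.2 sentence is a stray line, perhaps a loose way of saying the last parent-study value, and a sensible programmer would use Table 5. Much of this stands. A reader might infer that the OLE shift tables are undefined, and the documents do not support that: 5.4.3 and Table 5 give a baseline that can be computed. What remains is that two laboratory-specific rules disagree, no precedence is stated, and the one beside the shift-table specification cannot normally be followed.

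It is also fair to say that no text states that rollover subjects lack a parent EOS sample. Protocol 7.1.5 asks for final safety assessments in all subjects, and the windows can touch. The absence is a strong inference from the schedule, so a claim that every OLE subject has no baseline would go too far.

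The harm has limits. Observed values by visit, grade 3 or higher results, and out-of-range listings need no baseline, and efficacy is untouched. Accidental use of a post-OLE sample is a possibility only: 10.2 does name the parent study, and Table 5 bars post-dose values.

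Finally, a reader might take the Table 4 problem to spoil vital-sign shift tables. None is planned. SAP 10.3 only summarises vital signs at selected visits.

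**Conclusion.** The laboratory baseline sentence in SAP 10.2 is wrong as written and contradicts 5.4.3 and Table 5. On the nominal schedule of a full-length subject, the parent EOS falls 7 to 14 days after the first OLE dose, so following 10.2 would give a missing or post-dose baseline for the laboratory change-from-baseline and CTCAE shift tables. This rests on the inference that rollover subjects follow the schedule and have no parent EOS visit before OLE dosing.

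The defect is an unresolved contradiction, not a missing definition. The alternative rule works, with a baseline roughly 4 to 8 weeks old (28 to 63 days) if EOT falls at Week 104, 156 or 208. The age could reach about 18 weeks if transition can occur at any later dosing visit.

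The Table 4 wording is a smaller fault of the same kind, confined to vital-sign baseline summaries. The laboratory correction should be made, because it is nearly free and protects planned safety tables.

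**What to change.** 1. Delete the EOS sentence from SAP 10.2.
2. State there, and align 5.4.3 and Table 5 to match, that the laboratory baseline is the last available acceptable value on or before the first OLE infusion. The words last available matter: 5.4.3 now refers to the last visit, and the schedules mark no central laboratory sample at EOT or OLE Day 0.
3. Report the actual age of the baseline sample (for example, median and range of days before the first OLE infusion) rather than a fixed 4 to 8 week footnote, which could be wrong if transition weeks vary.
4. In Table 4, replace the baseline row with the pre-infusion value at the first OLE infusion or, if missing, the last value before it.

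The cost is a few lines of SAP text and one descriptive line in the tables. No new data are needed. The limitation that remains is a laboratory baseline that is some weeks old, and step 3 makes that visible.

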10.3. Vital Signs

Pulse (beat/min), diastolic and systolic blood pressure (mmHg), respiration (breaths/min), and temperature (C) will be summarized for selected analysis visit.

10.4. Physical Examination

Physical examination results (complete and targeted) will be listed by subject, visit, and body system.

10.5. Electrocardiogram

Number (%) of subjects with ECG results (normal/abnormal/Clinically Significant) will be summarized by analysis visit.

10.6. Special Safety Events

Treatment-emergent special safety events including:

1. Hypersensitivity (any time)
2. Infusion reactions (on day of infusion or 1 day post any study drug infusion)
3. Anaphylactic reactions (on day of infusion or 1 day post any study drug infusion)

Items 1 and 2 include both hypersensitivity and angioedema events. Both items will be listed and summarized similarly to TEAEs.

Items 3 uses a modified SMQ to retrieve events under anaphylactic reactions and will be listed and summarized by treatment and PT only.

The preferred term list for these special safety events will be finalized prior to database lock.

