### 2.3.3. Safety

Key findings are summarized below from the Phase 1 and 2 studies involving more than 400 adults with diabetic kidney disease, idiopathic pulmonary fibrosis, and liver fibrosis due to hepatitis B or pancreatic cancer:

- Overall, pamrevlumab was well tolerated across the range of doses noted above, and there were no dose-limiting toxicities.
- Treatment-emergent adverse events (TEAEs) were generally mild or moderate in severity and transient in duration.
- Infusion-related reactions have been mild-to-moderate and are considered an identified risk of pamrevlumab administration.
- TEAEs were considered typical of the subjects' underlying medical condition(s) and, in the placebo-controlled studies, were equally distributed between placebo and pamrevlumab treatment groups.
- No apparent pattern to TEAEs that occurred within 24 hours after infusions was observed.
- No apparent pattern for treatment-emergent serious adverse events (TESAEs) was observed during clinical testing.

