### **8.2.4. Acute Infusion Reaction**

An acute infusion reaction is one that meets both of the following criteria:

1. Occurs during or within 1 hour after infusion; and
2. Clinical manifestations consistent with:
  - a. IgE-mediated and non-IgE mediated hypersensitivity reactions, including but not limited to urticaria, skin rashes, angioedema, laryngeal edema, bronchospasm, gastrointestinal symptoms and hypotension; or
  - b. Cytokine release syndrome, including but not limited to fever, respiratory symptoms without the presence of wheezing, tremors, chills, flushing, pruritus, changes in blood pressure, dyspnea, chest discomfort, back pain, nausea, vomiting, diarrhea, and skin rashes.

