#### **8.2.4.1. Delayed Infusion Reaction**

A delayed infusion reaction is one that meets both of the following criteria:

1. Occurs  $\geq 1$  hour after the infusion
2. Clinical manifestations as described above.

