#### **8.2.4.2. Reporting Possible and Confirmed Infusion Reactions**

Both acute and delayed infusion reactions will be captured as AEs and also be reported to the medical monitor within 24 hours. See Study Reference Manual for additional details.

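### SAP 10.6 defines infusion reactions for the OLE more narrowly than Protocol 8.2.4 to 8.2.4.1, and SAP 13 does not declare the change

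*SAP*

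**What the plan says.** **SAP 10.6 (OLE period).** Three special safety events are listed. Item 1 is "Hypersensitivity (any time"), with no time limit. Item 2 is "Infusion reactions (on day of infusion or 1 day post any study drug infusion"). Item 3, anaphylactic reactions, has the same two-day window. On content, the section says "Items 1 and 2 include both hypersensitivity and angioedema events". On retrieval, it says "The preferred term list for these special safety events will be finalized prior to database lock". It does not mention cytokine release, an acute/delayed split, or reactions identified by the site.

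**Protocol 8.2.4 to 8.2.4.2.** An acute infusion reaction occurs during the infusion or up to 1 hour after it, with one of two clinical pictures. The first is hypersensitivity, whether or not IgE-mediated. The second, joined to the first by an "or" and sufficient alone, is "Cytokine release syndrome, including but not limited to fever, respiratory symptoms without the presence of wheezing, tremors, chills, flushing, pruritus", followed by further signs. For later onset, "A delayed infusion reaction is one that meets both of the following criteria": onset 1 hour or more after infusion, and the same manifestations. No upper time limit is given. On recording: "Both acute and delayed infusion reactions will be captured as AEs and also be reported to the medical monitor within 24 hours".

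**Status of the risk.** Protocol 2.3.3 states: "Infusion-related reactions have been mild-to-moderate and are considered an identified risk of pamrevlumab administration". Protocol 9.4.7 undertakes to list or tabulate infusion reactions separately.

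**Declared departures.** SAP 13 lists two changes from the protocol: the numbering of the first dosing day, and the added MMRM analyses. The infusion-reaction definition is not among them.

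**The concern.** The protocol and the SAP use one term for two different sets of events. Sites diagnose and report infusion reactions under the protocol definition. The clinical study report would tabulate, under the same name, a set built from a term list and a two-day window. The two counts need not agree, and nothing in the SAP warns the reader of that.

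This matters because infusion reactions are an identified risk, this is the first study of the drug in DMD (Protocol 2.4), and the protocol promises a separate presentation of them. A reader who wants the infusion-reaction incidence in the OLE will go to this table. Nothing in subject management is at stake: monitoring during infusions and access to home infusion depend on what sites observe, not on this table.

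**Working it through.** The plan gives no reaction rate and no distribution of onset times, so there is no figure of its own to reproduce. The check is a comparison of definitions, with one count of days.

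**Step 1: content.** The SAP gives items 1 and 2 the same content in one sentence. The only stated difference between them is time, so item 2 reads as item 1 restricted to the infusion day and the day after. The protocol's two clinical pictures overlap: skin rash is in both lists, and the gastrointestinal and blood-pressure signs are close. But fever, chills, tremors, flushing and back pain are named only under cytokine release. Those signs have no stated home in item 2.

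**Step 2: time.** With infusion day as day 0, four cases follow.

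| Reaction | Protocol 8.2.4 to 8.2.4.1 | SAP 10.6 item 2 | Where else it appears |
|---|---|---|---|
| Hypersensitivity type, day 0 or +1 | Infusion reaction | Counted | Item 1; TEAE tables |
| Hypersensitivity type, day +2 or later | Delayed infusion reaction | Outside the window | Item 1; TEAE tables |
| Cytokine-release type, day 0 or +1 | Infusion reaction | Depends on the final term list | TEAE tables |
| Cytokine-release type, day +2 or later | Delayed infusion reaction | Outside the window, whatever the list | TEAE tables; no special-event table unless the final list puts the term under hypersensitivity |

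The TEAE entries in the last column rest on SAP 10.1, which summarizes all TEAEs by system organ class and preferred term and lists all reported AEs.

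**Step 3: calendar coverage.** Dosing is every 2 weeks, or 14 days (SAP 2). The window covers the infusion day and the next day.

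- Covered: 2/14 = 14% of days.
- Not covered: 12/14 = 86% of days.

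This is a share of calendar time, not of expected reactions.

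**Step 4: can the open term list repair this?** In part. It could admit cytokine-release terms, which would settle the third row. It cannot change the stated window, so the second and fourth rows stay outside item 2. Nor can a term list separate a reaction from a coincidental fever or rash, or from an event caused by the process of infusing, which Protocol 8.2.3 keeps apart from infusion reactions. That needs the site's own identification.

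**Step 5: are the data there for a protocol-based table?** Acute and delayed reactions are captured as AEs (Protocol 8.2.4.2). The AE attributes in Protocol 8.3.2 include the date of onset, but no time of onset and no infusion-reaction flag. The acute/delayed boundary is 1 hour, which dates alone cannot resolve. Protocol 8.2.4.2 refers to a Study Reference Manual for details, and that manual is not among the documents.

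**The case against.** The strongest reply is that the SAP excludes very little outright. It says that the items include hypersensitivity and angioedema events, not that they consist only of them, and the term list is still open. Late hypersensitivity reactions are tabulated under item 1, and every TEAE is in the general tables. Protocol 9.4.7 asks only for a separate listing or tabulation, and item 2 is one. A calendar-day window is also a sensible way to work with AE records that carry dates but no times.

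Most of this stands, and it limits the point. Several stronger readings are tempting but not supported:

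- **That cytokine-release reactions are excluded by rule.** They are not provided for, which is different. Their omission is a likely result of the present text, not a stated rule.
- **That reactions disappear from the safety report.** They lose a label, not their place among the TEAEs.
- **That 12 of 14 days uncovered means most delayed reactions are missed.** The documents give no timing distribution. A per-subject figure such as 1/22 = 4.5 percentage points is no better: it assumes 22 OLE subjects, and a missed event in a subject already counted may change nothing.
- **That the table must understate.** The window and the named content push the count down, but a term search can also pull in coincidental infusion-day events. The net direction is not established.
- **That the whole study is affected.** This SAP covers the OLE. The main-study SAP is not among the documents, and the addendum names infusion reactions (Section 3.4.1) without defining them.

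What the reply does not answer is the window, which no term list alters, the absence of any stated use of site-identified reactions, and the silence of SAP 13.

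**Conclusion.** The two definitions conflict and should be reconciled before database lock. For the OLE, following SAP 10.6 as written means that a protocol-defined delayed reaction from day +2 onward cannot be labelled an infusion reaction, and that cytokine-release reactions have no stated place in the item. The consequence is a table of an identified risk that may not match what sites diagnosed.

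The number of reactions affected cannot be computed from the documents, and the sign of the net error is unproven. The conclusion assumes that the day +1 limit will be applied as stated and that site-identified reactions are not brought into item 2 by some route that the SAP leaves unmentioned. If the sponsor already plans such a route, the point reduces to writing it down.

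**What to change.** In SAP 10.6:

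1. Add, as the main infusion-reaction summary, the AEs that sites identified as infusion reactions under Protocol 8.2.4 to 8.2.4.2, whatever the preferred term or day. Split them into acute and delayed where the site's classification or the onset time is recorded.
2. Keep the term search over day 0 to +1 as a supplementary table, and add the cytokine-release terms of Protocol 8.2.4(b) to its list before database lock.
3. Record in SAP 13 how the term-based definition differs from the protocol's.

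The cost is SAP wording and one extra table. If the AE record carries no infusion-reaction flag, site reports to the medical monitor will have to be reconciled with the AE data, and the acute/delayed split may be incomplete. The reported incidence may rise.
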